7.2 Rationale

Results from the development programme of ivacaftor showed that ivacaftor was well tolerated, with the most common adverse events being typical manifestations of CF disease. In subjects who have a *G551D* mutation in at least 1 allele of the *CFTR* gene, the most common adverse reactions in subjects who received ivacaftor include abdominal pain, diarrhoea, dizziness, rash, upper respiratory tract reactions (including upper respiratory tract infection, nasal congestion, pharyngeal erythema, oropharyngeal pain, rhinitis, sinus congestion, and nasopharyngitis), headache, and bacteria in sputum. The most common serious adverse events in subjects receiving ivacaftor were CF exacerbations and haemoptysis, both of which are common manifestations of CF. Elevations of transaminases occurred in a small number of subjects in both the placebo and ivacaftor groups with similar incidence; the role of ivacaftor in contributing to transaminase elevations is uncertain, although data do not support an association. Based on the clinical safety database, the Risk Management Plan (RMP) identified several important potential risks, including the effect of long-term ivacaftor treatment on pulmonary exacerbation and bacterial sputum colonisation; off-label use (i.e., ivacaftor treatment in patients <6 years of age and patients who do not have the *G551D* mutation in the *CFTR* gene); effect of ivacaftor treatment in patients with forced expiratory volume in 1 second (FEV₁) <40% predicted value, cardiac disease, or hepatic impairment; and effect of ivacaftor treatment in pregnant or lactating women (see Kalydeco EU RMP).

Safety concerns identified in nonclinical studies that are not adequately addressed by clinical data include hepatotoxicity (repeat-dose toxicity studies in rats and mice), presence of ivacaftor in breast milk (radiolabelled ivacaftor study in pregnant and lactating rats), and cataracts (lens opacities identified in juvenile toxicology study in rats) (see Kalydeco EU RMP).

Efficacy results from the development programme showed that ivacaftor treatment targets the underlying pathophysiology of CF and has a broad array of benefits for subjects who have the *G551D* mutation in the *CFTR* gene. The Phase 3 studies showed that treatment with ivacaftor has systemic benefit, including substantial and durable improvements in pulmonary and extrapulmonary measures, with corresponding sustained improvements in CFTR function. The treatment effect in FEV₁ favored ivacaftor across all subgroups analysed.

Improvements in FEV₁ were persistent to 96 weeks of ivacaftor treatment. Notably, the efficacy of ivacaftor was observed whilst subjects continued on their prescribed therapies for CF. CF disease progression, as measured by pulmonary function or clinical signs, has not been studied beyond the ivacaftor clinical development programme. Therefore, there is a need to better understand the long-term effects of ivacaftor on pulmonary function as well as clinical signs of disease such as cystic fibrosis related diabetes (CFRD). This study will provide additional analyses on disease progression for up to 5 years.

Ivacaftor is intended for chronic, potentially lifelong use. Understanding of the long-term effects will be informative to patients and their parents, prescribers, and payers. Therefore, this post-authorisation safety study (PASS) will evaluate the identified potential risks of ivacaftor and CF disease progression in patients with CF who are treated with ivacaftor using observational cohorts of patients receiving ivacaftor in a "real-world" setting. Additionally, ivacaftor is indicated for patients 6 years of age and older who have the *G551D* mutation in the *CFTR* gene, without limitations on the patients' lung function. Hence, the patient population in this study will also include patients with minimal lung disease, a group on which there were limited data from the development programme of ivacaftor. The broader ivacaftor-exposed population available in this study will provide an opportunity to study CF disease progression as determined by pulmonary function and CF complications such as CFRD.

In the UK, the CF Trust has established a CF patient registry that states its main objective as to drive up standards of clinical care for patients with CF throughout the United Kingdom. As reported in the 2010 annual data report, the CF registry has enrolled over 9000 patients with CF, including 432 patients whose recorded genotype data have the *G551D* mutation.¹

In the US, the CF Foundation has established the CF Patient Registry that tracks the treatments and health of people with CF across the United States. As of the 2010 Annual Data Report, data have been collected on over 26,000 patients. Amongst patients with genotype reported, 1035 have the *G551D* mutation.²

In both patient registries, data collection is encounter-based with a comprehensive annual assessment of healthcare received and health outcomes. The Ivacaftor Long-term Safety Study, a PASS, will consist of analyses of safety and CF disease progression outcomes for ivacaftor-treated and comparator patients enrolled in the CF Trust and the CF Foundation patient registries.

8 RESEARCH QUESTIONS AND OBJECTIVES

8.1 Primary Objectives

1. To evaluate the long-term safety of ivacaftor in patients with CF
2. To evaluate outcomes of pregnancy in ivacaftor-treated patients
3. To evaluate the drug utilisation of ivacaftor
4. To evaluate CF disease progression in ivacaftor-treated patients

The comparisons to be made for each objective are described in Section 9.3.4 (Table 5).

8.2 Secondary Objectives

8.2.1 Secondary Objectives for Primary Objective 1

1. To evaluate the long-term safety of ivacaftor amongst patients in the following subgroups:
 - Patients between 6 and 11 years of age
 - Patients with FEV₁ <40% predicted value
 - Patients with cardiac disease
 - Patients with moderate or severe hepatic impairment
2. To evaluate pulmonary exacerbations and bacterial sputum colonisation with long-term ivacaftor treatment

8.2.2 Secondary Objective for Primary Objective 2

To measure the frequency of pregnancy in ivacaftor-treated patients

8.2.3 Secondary Objectives for Primary Objective 3

Off-label use amongst patients within the following subgroups:

- Children less than 6 years of age
- Patients with Class III, non-*G551D-CFTR* mutations
- Patients with non-Class III mutations

8.2.4 Secondary Objectives for Primary Objective 4

To evaluate the effect of ivacaftor on CF disease progression, as measured by

- CF lung disease severity, based on pulmonary function (e.g., percent predicted FEV₁)
- Clinical signs of CF disease progression (e.g., death, transplantation, CFRD, distal intestinal obstruction syndrome [DIOS])
- Change in lung function over time

8.3 Prior Hypotheses

The purpose of this study is to perform analyses that will inform us on the long-term safety of ivacaftor use in patients with CF. Given the known safety profile of ivacaftor, this study will further characterise the safety of chronic ivacaftor treatment in real-life use and provide descriptive analyses on specified safety and CF disease progression outcomes using observational data. These analyses will be used for hypothesis generation for safety issues that warrant future study. Therefore, no prior hypotheses are proposed for the primary objectives. Prior hypothesis is provided for specific secondary objectives, although the study may be underpowered to detect any differences:

- Pulmonary exacerbations: similar or lower incidence in the Ivacaftor Cohort than the Comparator Cohort and previously observed in the pivotal Phase 3 studies (as described in the Summary of Product Characteristics [SmPC])
- Adverse drug reactions (as listed in the SmPC): similar or lower incidence in the Ivacaftor Cohort than the Comparator Cohort and previously observed in the pivotal Phase 3 studies (as described in the SmPC)
- Serious adverse events and adverse events leading to withdrawal of ivacaftor: similar or lower incidence in the Ivacaftor Cohort than the Comparator Cohort (CF Trust data only).

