Observational or noninterventional study design is the preferred method used to understand the safety of products in the "real-world" setting and allows for data collection of outcomes without influencing treatment patterns. Once market authorisation is achieved, it is expected that a broader patient population will be exposed to the drug compared to the population exposed in the clinical development programme. The observational design allows for the study of outcomes in the newly exposed population and, because of the availability of historical data for patients enrolled in the registries, previously exposed patients. With this design, we estimate that a subset of patients who were exposed to ivacaftor during clinical development and continue to be treated with ivacaftor will have exposure durations of greater than 5 years when analysed for the annual reports.

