The Class III *CFTR* mutations include *G551D*, *G178R*, *S549N*, *S549R*, *G551S*, *G970R*, *G1244E*, *S1251N*, *S1255P*, *G1349D*, and *R560T* (see also RMP).¹⁴ Because of the low prevalence of Class III mutations (<5% overall with approximately 1% representing non-*G551D* mutations), it will not be possible to match patients with the *G551D* mutation to patients with other Class III mutations. The following matching scheme for genotype will be implemented.

- Any Class III *CFTR* allele will be matched to *F508del*, a mutation in a different class (Class II) but of similar phenotype (similar sweat chloride levels, FEV₁, forced vital capacity, height, weight, pancreatic sufficiency, and incidence of *Pseudomonas aeruginosa* colonisation).^{14,22} For example, a patient with *CFTR* alleles of *G551D/F508del* will be matched to a patient with *CFTR* alleles of *F508del/F508del*.
- Alleles in *CFTR* Classes I and II will be matched to Class I or II; alleles in *CFTR* Classes IV and V will be match to Class IV or V.

This scheme will allow for patients with a second allele associated with less severe phenotype (e.g., Class IV or V) to be matched to a patient with a similar genotype and not a more severe class (e.g., Class I to III). Patients with an allele of unknown genotype (meaning mutation has not yet been identified) or a mutation of unknown mutation class will be matched to *F508del*.

The genotype matching algorithm is provided in Figure 1.

Figure 1 Genotype Matching Algorithm

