9.2.5 Other Matching Considerations

Given the limited size of the CF population, the Comparator and Comparator Pregnancy Cohorts will not be matched for other measures of disease severity (e.g., percent predicted FEV₁, *Pseudomonas aeruginosa* infection) due to concerns about availability of adequate patients for matching. However, measures of disease severity will be included as stratification variables and as covariates for adjustment, as necessary.

The Historical Cohort will include patients with a *G551D-CFTR* mutation who were in the patient registries in 2008. These patients were chosen because they represent the best match to ivacaftor-treated patients in 2012 and later because they match the indicated patient population based on the approved product labelling. The Historical Cohort will include patients of all ages and will be stratified to identify outcomes for patients younger than 6 years of age (for the potential off-label population). The year 2008 was chosen because starting in 2009, ivacaftor clinical studies were actively enrolling in the UK and US. A 1-year window was selected to match the window for safety outcome analysis in the Ivacaftor and Comparator Cohorts. The Historical Cohort will be analysed once for Objectives 1 and 2 for all stratification variables. If additional analyses are identified during the conduct of the study, the Historical Cohort will be available for analysis.

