9.3.2.3 Analysis Variables

Age will be defined using date of birth.

Sex will be defined as reported in database.

Genotype will be defined for each allele and will be categorised by *CFTR* mutation class.^{14,22}

Baseline percent predicted FEV₁ will be defined by most recent value obtained before initiating ivacaftor in the Ivacaftor Cohort; percent predicted FEV₁ will be matched to the most recent available value by calendar date for the Comparator Cohort. Standardised equations (those of Hankinson et al.³⁰ or Wang et al.³¹ [see Section 9.3.4.4]) will be used to calculate percent predicted FEV₁ and will be specified in the statistical analysis plan (see [Stand-alone Document 4](#) listed in Annex 1. List of Stand-alone Documents). Analysis of FVC and FEF_{25%-75%} will also be specified in the statistical analysis plan.

Cardiac disease will be defined by evidence of cardiac disease in reason for hospitalisation or in specified CF complications.

Hepatic impairment will be defined by liver disease with complications (e.g., cirrhosis complications: oesophageal varices, gastric varices, GI bleed, splenomegaly, hypersplenism, ascites).

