9.3.4 Statistical Analyses

Data analyses will be performed by the CF Trust and CF Foundation to meet the study objectives. The results of the annual analyses will be reported in the study report.

The primary objectives of this study are to evaluate long-term safety, pregnancy outcomes, drug utilisation, and CF disease progression in patients treated with ivacaftor. Descriptive statistics will be calculated for all endpoints. All safety, pregnancy, and CF disease progression endpoints will be compared between the Ivacaftor and Comparator Cohorts or between the Ivacaftor Pregnancy and Comparator Pregnancy Cohorts. Safety and pregnancy outcomes will also be described for the Historical Cohort. Annual incidence rates will be calculated for safety outcomes (Objective 1). Crude relative risks or risk difference with 95% confidence intervals will be calculated for some outcomes, as appropriate. Statistical modelling with adjustment for confounders and effect modifiers will be conducted, as possible, due to the likely sparse data. Identification of confounders and effect modifiers will be performed using stratified analyses. Each annual report will include the patient data from the previous calendar year (e.g., annual cross-sectional analysis). Longitudinal analyses will be included, as appropriate, in the final report.

This section presents a summary of the planned statistical analyses for this study (see [Stand-alone Document 4](#) listed in Annex 1. List of Stand-alone Documents). A detailed

analysis plan will be presented in a statistical analysis plan. A summary of the comparisons to be made for each objective is provided in Table 5.

Table 5 Comparisons by Primary Objective

Objective	Setting	Cohorts Included	Comparisons
1. To evaluate the long-term safety of ivacaftor in patients with CF	UK, US	Ivacaftor; Comparator; Historical	
 Comparison of long-term safety between the Ivacaftor Cohort (ivacaftor-treated patients) and the Comparator Cohort (concurrent nonexposed patients) to include relative risks or risk differences Descriptive statistics for the Historical Cohort (historical nonexposed patients) will be available for comparison to the Ivacaftor Cohort (ivacaftor-treated patients). Comparisons to be based on 95% confidence intervals.

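### The annual Ivacaftor-versus-Comparator contrast for exacerbations, hospitalisations and respiratory microbiology uses no pre-ivacaftor value of the outcome, so a pre-existing cohort difference cannot be separated from a drug effect

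*Protocol*

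**What the plan says.** Section 8.3 gives a directional expectation for a few outcomes, the first being "Pulmonary exacerbations: similar or lower incidence in the Ivacaftor Cohort than the Comparator Cohort". It proposes no hypotheses for the primary objectives and says "These analyses will be used for hypothesis generation for safety issues that warrant future study".

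The contrast is built as follows:

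- **Genotype (Section 9.2.4).** A Class III allele "will be matched to *F508del*, a mutation in a different class (Class II) but of similar phenotype". The similarity listed covers sweat chloride, FEV1, FVC, height, weight, pancreatic sufficiency and *P. aeruginosa* colonisation. Section 9.2.3 explains the choice: few untreated G551D patients are expected to remain.
- **Severity (Section 9.2.5).** "the Comparator and Comparator Pregnancy Cohorts will not be matched for other measures of disease severity"; severity measures may serve as strata or covariates where needed.
- **Window and measure (Section 9.3.4).** Each annual report covers the previous calendar year. "Crude relative risks or risk difference with 95% confidence intervals will be calculated for some outcomes, as appropriate".
- **Strata (Section 9.3.4.1).** Exposure duration, age, sex, genotype class, percent predicted FEV1 and comorbid conditions.
- **Candidate confounders (Section 9.3.5).** An open list that includes pulmonary function, microbiology, concomitant medication, pancreatic and diabetes status, and health care utilisation.
- **Baseline (Sections 9.3.1.3 and 9.3.2.3).** Percent predicted FEV1 is the "most recent value obtained before initiating ivacaftor in the Ivacaftor Cohort", with a calendar-matched value for comparators.
- **Other references.** A 2008 untreated G551D Historical Cohort, analysed once for Objective 1 (Section 9.2.5), and longitudinal analyses in the final report (Section 9.3.4).

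**The concern.** The listed phenotypic similarity does not include exacerbation or hospitalisation rates, yet those are the outcomes compared. If G551D patients, or those who start ivacaftor, already differed from F508del comparators on these outcomes, the on-treatment ratio is the product of that earlier ratio and any drug effect. Nothing stated in the protocol lets a reader factor the two.

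For a safety study the more serious direction is masking: a favourable starting difference could hide a harmful effect. The opposite difference could raise a false signal, or make the Section 8.3 expectation fail with no drug effect. More patients would not help, because this is bias rather than imprecision.

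**Working it through.** **1. The plan's own figures.** The only power figures are in Table 6, for death. Enumerating the one-sided Fisher exact test (alpha 0.1, equal groups, 0.011 in the unexposed) gives 0.386 and 0.706 at relative risk 2 for N = 432 and 1,035 (stated 0.393 and 0.703). At relative risk 3 it gives 0.769 and 0.982 (stated 0.772 and 0.981). Table 6 reproduces, with a largest gap of about 0.007. It does not cover recurrent non-fatal outcomes, so it neither supports nor weakens this point.

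**2. Does anything stated supply the missing reference?**

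- *Historical Cohort.* G551D only. With no 2008 F508del group, the pre-existing Class III to F508del ratio is not estimated. Section 9.9 adds that care and data fields have changed since.
- *Longitudinal analyses.* Their content for safety outcomes is not stated. The one described in detail, lung function in Section 9.3.4.4, requires ivacaftor exposure in every year analysed, so its first year is already on treatment.
- *Health care utilisation.* No pre-start period is given. Section 9.9 counts hospitalisations within it, and hospitalisation is itself an outcome. Measured on treatment, it cannot stand for baseline risk.
- *Pre-start FEV1.* Helpful, but it is not the outcome's own history.

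**3. Size of the distortion.** Observed ratio = pre-existing ratio × true drug ratio.

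| Pre-existing ratio | Observed, true 1.00 | Observed, true 1.25 |
|---|---|---|
| 0.8 | 0.80 | 1.00 |
| 0.9 | 0.90 | 1.125 |
| 1.0 | 1.00 | 1.25 |
| 1.1 | 1.10 | 1.375 |
| 1.2 | 1.20 | 1.50 |

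**4. Chance that a crude 95% interval excludes 1 with no drug effect.** From Section 9.5: n = 432 (UK) and 1,035 (US). Assumed, because the documents give no values: m = 5 comparators per patient, μ = 0.5 to 0.8 events per patient-year, negative binomial dispersion k = 1.

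Var(log RR) = (1/μ + k)/n × (1 + 1/m)

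- US: √(3 × 1.2/1035) = 0.059 at μ = 0.5; √(2.25 × 1.2/1035) = 0.051 at μ = 0.8.
- UK: √(3 × 1.2/432) = 0.091; √(2.25 × 1.2/432) = 0.079.

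P = Φ(|log r|/SE − 1.96) + Φ(−|log r|/SE − 1.96)

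- r = 0.90 (|log r| = 0.105): 43-54% US, 21-27% UK.
- r = 0.85 (|log r| = 0.163): 79-89% US, 43-54% UK.

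**5. Same question with yes/no data,** which is how Table 4 lists exacerbations. Assume 30-50% of comparators have at least one exacerbation a year, with a two-sided test at 0.05.

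| Pre-existing ratio | Allocation | N = 432 | N = 1,035 |
|---|---|---|---|
| 0.9 | 1:1 | 16-31% | 33-63% |
| 0.9 | 5:1 | 23-48% | 49-84% |
| 0.8 | 1:1 | 51-84% | 87-99.6% |

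The nominal figure is 5%.

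**6. What each remedy does.** Assume a correlation ρ = 0.5 between prior-year and current values with similar variances.

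- *Covariate adjustment alone.* The slope is about 0.5, so a stable gap g shrinks only to g − 0.5g = 0.5g. It also removes ρ² = 25% of the outcome variance.
- *Ratio of on-treatment to prior-year ratios.* This cancels a stable gap and returns the true ratio (1.00 or 1.25) in every row of step 3, if trends are parallel. Its variance on the log scale is about 2(1 − ρ) times that of the single-year ratio: equal at ρ = 0.5, and 1.4 times at ρ = 0.3.

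**The case against.** The case on the other side is substantial.

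- **A reader might infer that the plan credits any cohort difference to ivacaftor.** The documents do not support that. Section 8.3 calls the analyses descriptive and hypothesis-generating and warns of low power. Section 9.9 concedes that treated patients may differ systematically, and it lists limits specific to the exacerbation hypothesis. What stands is that the two sources of difference cannot be separated.
- **A reader might infer that only analysis-year data are used.** That is also too strong, given the Historical Cohort, the final-report longitudinal analyses and pre-start FEV1. As step 2 shows, though, none of them gives the cohort contrast a pre-treatment value of the outcome.
- **Covariates and look-back windows are ordinary SAP content,** and Section 9.3.5 is an open list. This has force and limits the point to a recommended improvement. But the protocol itself fixes the comparison, the window and the strata, and it defines a pre-initiation baseline for percent predicted FEV1 but not for these outcomes.
- **Prior-year data may not be clean.** Section 9.1 says previously exposed patients can be studied "because of the availability of historical data for patients enrolled in the registries". That sentence is about patients treated in earlier trials, some of whom will lack an untreated prior year close to the study, and Section 9.9 says registry fields have changed. Both stand as limits. Against them, the registries will extract 2008 outcomes anyway, and Section 9.6.2 reports 91% completeness in 2011 for both complications and microbiology in the US.
- **The probabilities are illustrative.** This stands in full. Section 9.5 also calls 432 and 1,035 a best case, so smaller cohorts would give lower figures.

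**Conclusion.** The point holds in a limited form. For pulmonary exacerbations, hospitalisations and respiratory microbiology, the annual Ivacaftor-versus-Comparator contrast crosses genotypes, is unmatched on severity, and has no pre-ivacaftor value of the outcome. The similarity assumed in Section 9.2.4 is therefore not checked for these outcomes. Section 8.3's other benchmark, the Phase 3 studies, does not fill the gap, because Section 9.9 says exacerbations are collected in a way that does not allow direct comparison.

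The documents do not show that a pre-existing difference exists, nor which way it would run. If one of 10% existed, the assumed rates give nominally significant results with no drug effect in 43-54% (US) and 21-27% (UK) of annual analyses. The yes/no model with five comparators per patient gives 49-84% and 23-48%. These figures rest on assumed event rates, dispersion and matching ratio, and on best-case cohort sizes.

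This is an improvement worth making, not an error that invalidates the study.

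**What to change.** In Sections 9.3.4.1 and 9.3.5, for these three outcomes:

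1. Using the index date already defined for baseline FEV1, extract the last full calendar year before ivacaftor start for each treated patient and the matched comparators.
2. Print the prior-year cohort ratio beside each on-treatment ratio, and report on-treatment ratio divided by prior-year ratio with its 95% confidence interval. State that it assumes parallel trends and can be affected by regression to the mean, for example if patients start ivacaftor after an unusually bad year.
3. As a secondary analysis, adjust for the patient's own prior-year value, yes/no or count as recorded. Alone, this removes only part of a stable gap.
4. Measure the health care utilisation covariate of Section 9.3.5 in that same pre-start year.
5. Show patients with no usable prior year (trial-exposed, newly registered, very young) as a separate row.

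Cost: one extra extraction year from the same registries and a few added columns. A comparator matched to several treated patients may need more than one index year, and some patients will have no prior-year record. If the prior-year correlation is below 0.5, the ratio of ratios will have a wider interval than the single-year ratio.

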9.3 Variables

All variables for study endpoints are collected in prespecified data collection forms. For example, specific diagnoses are captured as data elements rather than as a collection of information from which a diagnosis would be made. Adjudication is done by the governing committees of the patient registries. Investigators (physicians with expertise in CF) from certified CF centres complete the forms according to the data guidelines and indicate the specified diagnoses for patients. Because verbatim terms are not reported and forms contain adjudicated diagnoses, the data are inherently coded. Each registry employs its own data entry guideline rather than use external coding dictionaries.

The CF Trust and CF Foundation patient registries employ data collection instructions and rigorous data cleaning procedures to provide robust data sets for the analysis of ivacaftor safety, drug utilisation, and CF disease progression. The principal investigators of this protocol are both physicians with expertise in CF, familiar with the current standards for treating patients with CF, as well as the data quality process of their respective registries. Therefore, an external expert committee for validation of diagnoses is not planned.

The CF Trust and CF Foundation independently determine the data to be collected; thus, the specific variables included in the analyses for this study are not necessarily identical. Types of variables important for this analysis include exposure, outcomes, and stratification variables. Stratification variables will be explored to identify confounders and effect modifiers. Data are collected for each patient registry; therefore, variables are described separately (Sections 9.3.1 and 9.3.2). Table 4 provides a comparison of the variables to be collected.

Table 4 Comparison of Variables Collected by the Patient Registries

Variables	CF Trust (UK)	CF Foundation (US)
Exposure	start/stop (reason)	yes (150 mg/other)/no
Prior ivacaftor exposure	Derived based on start date before January 2013	Derived based on ivacaftor exposure in 2012
Death	date; cause (respiratory/ cardiorespiratory, liver disease, trauma, suicide, transplant-related, other)	date; cause (respiratory/ cardiorespiratory, liver disease, trauma, suicide, transplant-related, other, unknown)
Organ transplantation	yes (lung, other)/no	yes (lung, liver, kidney, other)/no

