Given the scientific interest in the assessments of pulmonary exacerbations and adverse events in the CF population, a null hypothesis would be that there is no difference in the incidence of these events between Ivacaftor and Comparator Cohorts or perhaps a lower incidence in the Ivacaftor Cohort. However, the analyses are limited by a number of factors. The lack of knowledge on the background risk of specific adverse events in the target CF population means that it is not possible to predict whether the number of patients in each registry will be sufficient to power the detection of statistically significant differences between the Ivacaftor and Comparator Cohorts. The small sample size may also lead to spurious results that may confound interpretation, and the manner in which pulmonary exacerbations are collected do not allow direct comparison to the incidence of pulmonary exacerbation observed in Phase 3.

For the specific prior hypothesis on pulmonary exacerbation, the CF Trust and CF Foundation registries do not predefine the clinical presentations that constitute a pulmonary exacerbation. Therefore, there is likely some variability in pulmonary exacerbation events within each registry and across both registries. Further, because the data sets are based on existing registry variables, adverse drug reactions, and adverse events in the SmPC will rely on mapping variables and/or rely on CF care centres providing text entries that are mappable.

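### The protocol expects adverse reactions to be no more frequent than in Phase 3, but the registries have no variable for five of the seven reaction groups it names, so non-collection alone can meet that expectation.

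*Protocol*

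**What the plan says.** Section 8.3 sets no hypotheses for the primary objectives but gives three for secondary ones. The second reads "Adverse drug reactions (as listed in the SmPC): similar or lower incidence in the Ivacaftor Cohort than the Comparator Cohort and previously observed"; the sentence then names Phase 3 as that second reference. The abstract repeats it. No margin is given for similarity, and the list is introduced with the reservation "although the study may be underpowered to detect any differences".

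Section 7.2 names the most common reactions. They "include abdominal pain, diarrhoea, dizziness, rash, upper respiratory tract reactions (including upper respiratory tract infection, nasal congestion" and other upper respiratory terms, then "headache, and bacteria in sputum".

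On data, section 9.3 says "All variables for study endpoints are collected in prespecified data collection forms" and adds "Because verbatim terms are not reported and forms contain adjudicated diagnoses, the data are inherently coded". The outcome lists are in sections 9.3.1.2 (UK) and 9.3.2.2 (US). Section 9.9 says that adverse drug reactions and SmPC adverse events "will rely on mapping variables and/or rely on CF care centres providing text entries that are mappable". The same subsection states that the way exacerbations are collected rules out a direct comparison with Phase 3. It says nothing of the kind for adverse reactions.

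**The concern.** The hypothesis has two reference points: concurrent untreated patients and the Phase 3 incidence. Both cohorts come from the same registries, so poor recording at least acts on both sides of the first comparison. In the second it acts on one side only. If a symptom has no box on the registry form, its recorded incidence is governed mainly by whether someone happens to write it in, and a figure below Phase 3 says little about the drug.

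Section 12 says the results will be used to adjust the safety specification and pharmacovigilance plan of the Risk Management Plan. A finding of lower incidence than in Phase 3, produced by missing fields, could be read there as reassurance.

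**Working it through.** **Step 1: reactions against registry variables.** The SmPC list is not in the protocol, so the section 7.2 list stands in for it. It is set against Table 4 and sections 9.3.1.2 and 9.3.2.2.

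| Reaction group (7.2) | UK variable | US variable |
|---|---|---|
| Abdominal pain | none | none |
| Diarrhoea | none | none |
| Dizziness | none | none |
| Rash | none | none |
| Headache | none | none |
| Upper respiratory tract reactions | sinus disease (partial) | sinus disease; sinus-infection admission (partial) |
| Bacteria in sputum | respiratory microbiology | respiratory microbiology |

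Five of seven have no variable, one has partial proxies and one is covered. The five can enter only through the free-text entry for other complications. The UK reason for stopping treatment (9.3.1.1) has a generic side-effect category that names no reaction.

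**Step 2: the plan's own figures.** The only power figures are in Table 6, and they concern death. Under the stated test (one-sided Fisher exact, alpha 0.1, equal groups) all 24 cells reproduce within 0.01. At a relative risk of 2 the recomputed power is 0.386 (N = 432) and 0.706 (N = 1035), against 0.393 and 0.703 in the table. No figure exists for adverse reactions.

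**Step 3: the Phase 3 limb.** Let p be the Phase 3 incidence, r the true ratio of ivacaftor incidence in the registry to p, and c the fraction of events that reach the registry, relative to Phase 3 recording. Expected recorded incidence is c × r × p. It lies below p whenever c < 1/r. For r = 2 that is any capture below 0.50, whatever p is.

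For the probability, take recorded events as binomial with N = 432 (UK) or 1035 (US), the registry counts in section 9.5, and success probability c × r × p. Treat p as fixed. The values of p and c are assumptions, since the protocol gives neither.

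Least favourable case with p from 5% to 15%, r = 2 and c = 0.30 (UK, p = 0.05):
- recorded rate 0.30 × 2 × 0.05 = 0.03, so 432 × 0.03 = 12.96 events expected;
- Phase 3 level 432 × 0.05 = 21.6, so 21 or fewer events count as at or below it;
- probability 0.988.

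| Capture c (r = 2, p = 5% to 15%) | P(recorded at or below Phase 3), both registries |
|---|---|
| 0.20 or less | about 1.00 |
| 0.30 | at least 0.988 |
| 0.50 | about 0.5 |

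At full capture the probability of falling below Phase 3 is about 0 (computed for p of 5%, 10% and 20%). A true tripling at c = 0.20 still falls below Phase 3 with probability of at least 0.988.

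**Step 4: the comparator limb.** If capture is equal in both cohorts, the expected ratio is (c × r × p) / (c × p) = r. The relative risk is roughly preserved and only the event count shrinks. With p from 5% to 15%, r = 2, c = 0.20 and a Wald 95% interval for the log relative risk, the chance of seeing no significant excess is:

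| Matching | UK | US |
|---|---|---|
| 1:1 | roughly 45% to 84% | roughly 9% to 55% |
| 5:1 (assumed) | roughly 18% to 59% | roughly 1% to 28% |

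The protocol matches at the maximum number of comparators available (sections 9.1.1 and 4), so 1:1 is pessimistic. Power suffers, but a doubling can still show.

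**The case against.** The strongest defence is that nothing is formally tested. Section 8.3 calls the analyses descriptive and hypothesis-generating, concedes low power and sets no success rule. Adverse reactions are not among the six safety categories of section 9.3.4.1, and Table 5 lists no Phase 3 comparison. Section 9.9 already warns about mapping, and the mapping itself could sit in the statistical analysis plan. The SmPC list and the registry questionnaires are not shown, so the field count rests on the protocol's own summary.

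Much of this stands: the point concerns a secondary, descriptive hypothesis, and the section 7.2 list is a stand-in. It does not remove the problem. The study collects no primary data (9.1) and the registries decide independently what they record (9.3), so an analysis plan cannot create missing fields. The caveat in section 9.9 does not say that under-recording favours the hypothesis, and it withdraws the Phase 3 comparison only for exacerbations. The next bullet in section 8.3 shows that a narrower form was available: serious events and withdrawals are limited to UK data and carry no Phase 3 reference.

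A reader might go further and infer that the whole hypothesis is met almost whatever ivacaftor does, against comparators as well. The documents do not support that. Equal under-recording leaves the relative risk roughly intact, matching is not limited to 1:1, and reactions with a field can contradict the hypothesis. Recording may also differ between cohorts: fuller recording in patients on a new drug would push the result against ivacaftor. The direction of bias on that limb is unknown.

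**Conclusion.** The concern holds for the Phase 3 limb. For five of the seven reaction groups the protocol names, recorded incidence can be below Phase 3 simply because the registries do not collect the event. The 50% threshold for hiding a doubling is arithmetic and needs no assumed incidence. The probability of about 0.99 or more rests on assumed capture of 30% or less, reference incidence of 5% to 15%, and 432 and 1035 treated patients, which section 9.5 presents as a best case. Actual capture is unknown; near 50% the result would be close to a coin toss.

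For the comparator limb the conclusion is only that power is reduced and that differential recording could bias the result either way. Sections 9.3 and 9.9 also pull against each other on whether text entries are available. The point should be corrected, but it bears on a secondary descriptive hypothesis and not on the main safety endpoints.

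**What to change.** In section 8.3 and the abstract:

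- Delete the comparison of adverse reactions with Phase 3 incidence.
- Limit the comparator hypothesis to reactions with a named registry variable: respiratory microbiology for bacteria in sputum, with sinus disease (both registries) and sinus-infection admission (US) as declared partial proxies for upper respiratory reactions.
- State that abdominal pain, diarrhoea, dizziness, rash and headache are not evaluable for incidence. Free-text reports are descriptive: counts, with any relative risk against comparators labelled exploratory. Their absence or low frequency is not evidence of safety.

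Reconcile section 9.3, which says verbatim terms are not reported, with section 9.9, which relies on text entries.

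The cost is protocol wording and somewhat less tabulation. The study openly gives up part of a secondary descriptive hypothesis that it cannot assess; comparator estimates from free text remain available for signal generation.
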